identified by Palmetto Health Physical Therapists will be provided information about the study verbally by a USC research staff member. Interested patients will be able to ask questions and read the consent form. They will have the opportunity to complete the informed consent process either at the first or second outpatient physical therapy appointment.

b. Inclusion and Exclusion Criteria

After initial identification of potential patient participants by physical therapists, research staff will screen patients for eligibility criteria in-person or over the telephone.

Inclusion criteria:

Eligible participants will 1) be 40-79 years of age, 2) have had a knee replacement in the last 2 months, 3) be willing to wear an accelerometer for 7 days during assessments, and 4) be English speaking.

Exclusion criteria:

As all patients will be under physicians' supervision post-TKR, participants will only be excluded if they (1) have any contraindications to activity, (2) have a mobility limiting comorbidity (e.g. spinal stenosis), or (3) have a scheduled surgery (i.e., TKR on contralateral knee) within the next 6 months.

c. Local Number of Subjects

We will aim to randomize 50 patients that had a knee replacement within the last 2 months and are attending outpatient physical therapy at the Palmetto Health USC Orthopedic Center. We anticipate that we will need to approach and screen approximately 75 patients to enroll our goal of 50 patients.

d. Study-Wide Number of Subjects

NA

e. Study Timelines

Subject participation will last 12 weeks. We estimate it will take 15 months to complete the study, which will include finished study enrollment, data collection and data analysis (See Figure 1).

Figure 1. Project Timeline

	Project Month														
	1	2	3	4	5	6	7	8	9	10	11	12	13	14	15
Finalize protocol & IRB approval	X	X	X												
Recruit TKA patients (n=50)				X	X	X	X	X	X	X	X	X	X		
Intervention				X	X	X	X	X	X	X	X	X	X		
Completing 12 week assessments				X	X	X	X	X	X	X	X	X	X	X	
Data Analysis														X	X
Prepare manuscript & presentations														X	X
Draft & submit NIH R21 or R01														X	X

f. Study Endpoints

[figure not shown]

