Assessments will be completed before the second outpatient therapy session (baseline) and at 12 weeks after TKR. Detailed descriptions and a timeline of outcomes are provided below in the text and Table 2. Briefly, at both assessments, participants will be asked to complete surveys (demographics, brief medical history, KOOS, PROMIS, self-identification), which should take approximately 20 minutes to complete. Based on participant preferences, surveys will be able to be completed on paper or online via RedCAP, with the exception of the PROMIS surveys which are computer adaptive surveys. Participants will also be given an Actigraph Link accelerometer and ActivPAL monitor to wear for 7 days at each assessment. These monitors will be provided at the in-person assessment or mailed to the participants. At the end of the 7 days, these monitors will be returned to the PT clinic or participants will be provided with a prepaid padded envelope to return the monitor. Only at 12 weeks will participants complete functional tests and the Surgery and Medication Questionnaire, which will take approximately 15 minutes to complete. In the event participants are unable to complete the function tests at the in-person assessment, we will ask participants to complete the chair stand test at home and self-report the outcomes. Participants will not be asked to complete the 6-minute walk or timed up and go at home. Participants will receive \$20 for completing the 12-week assessment.

Measure	Baseline	12 Weeks
Participant Demographics	X	
Participant height and weight	X	X
Brief Medical History	X	X
Knee Injury and Osteoarthritis Outcome Score (KOOS)	X	X
PROMIS Pain Intensity, Pain Interference, & Mobility	X	X
WOMAC Pain and Stiffness	X	X
Physical Function		
6-minute walk		X
Timed up and go		X
Chair stands		X
Physical activity (Actigraph)	X	X
Sedentary time (ActivPAL)	X	X
Self-Reported Exercise Identity	X	X
PATH Study Survey		X

Primary Outcomes: The feasibility and acceptability of conducting a randomized controlled trial within an outpatient physical therapy setting is the primary endpoint. Specifically, we will examine the number of participants enrolled vs. approached, participant retention, number of therapy sessions attended, session duration, and treatment fidelity. Further, participants will complete a PATH Study Survey at the 12 week assessment. Physical therapists will complete a brief evaluation about delivering the PATH program.

Secondary Outcomes:

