- Self-reported exercise identity will be assessed at baseline and 12-week assessments using the Self-Reported Exercise Identity Scale.³³ Participants will rate on a scale from 1 (strongly disagree) to 5 (strongly agree) their feelings relating to exercise identity. Examples include, “I would feel a real loss if I were forced to give up exercising” and “I need exercise to feel good about myself.”

g. Procedures Involved

Design Overview: We propose to conduct a pilot two-arm cluster randomized controlled trial with patients attending outpatient physical therapy following TKR. The proposed project was developed in collaboration with [name], Senior Physical Therapist at Palmetto Health USC Orthopedic Center. Over 9 months, TKR patients (n=50) attending outpatient physical therapy at Palmetto Health USC Orthopedic Center will be recruited and randomized to either 1) PATH-12 (control), or 2) PATH. Due to potential contamination of the intervention between patients in PATH-12 and PATH during typical open, group-like physical therapy settings, we have opted to randomize physical therapy sites instead of individual patients. Specifically, physical therapy sites will be randomized to either Immediate or Delayed. The first phase of the study will take place starting in November and end after 25 participants have been recruited. During this time, those sites randomized to Immediate will receive the PATH intervention and those sites randomized to Delayed will receive the PATH-12 intervention. There will then be a “wash out period” to allow for all the participants to finish their current PT. After this “wash out period”, the second phase of the study will begin and will end after 25 participants have been recruited. During this time, those sites randomized to Immediate will receive the PATH-12 intervention and those sites randomized to Delayed will receive the PATH intervention.”

Screening: Participants will be required to complete a brief screening after the first physical therapy appointment. Research staff will administer the screening in-person or over the telephone. The screening will assess eligibility criteria and willingness to participate. Following the completion of the screener, eligible and interested participants will be invited to complete the informed consent process.

Randomized Conditions:

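### Figure 1 leaves one month between last recruitment (month 13) and the close of 12-week assessments (month 14), too short for the protocol's own follow-up under almost every permitted entry time

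*Combined protocol and SAP*

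**What the plan says.** Section 7e gives the overall schedule: "Subject participation will last 12 weeks. We estimate it will take 15 months to complete the study". Figure 1 in that section marks recruitment of the 50 patients in months 4 to 13, the intervention in months 4 to 13, the row "Completing 12 week assessments" in months 4 to 14, and data analysis in months 14 and 15.

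Section 7f uses a different clock for follow-up. Assessments take place "before the second outpatient therapy session (baseline) and at 12 weeks after TKR", with 7 days of monitor wear each time. Under section 7b a patient may enter up to two months after surgery.

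Section 7g (Design Overview) says recruitment takes 9 months. It is split into two phases of 25 patients, separated by a washout "to allow for all the participants to finish their current PT". No length is given for the washout, and Figure 1 has no row or gap for it. Section 5 describes the 15 months as the grant-funded period.

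**The concern.** The chart allows one month between the last possible entry and the close of 12-week assessments. A patient followed for 12 weeks needs almost three months. A patient followed to 12 weeks after surgery needs somewhere between about 3 and 12 weeks, depending on when he or she entered.

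The Intervention row has a related problem. It stops in the same month as recruitment, although the background text gives outpatient rehabilitation as 4 to 6 weeks and the intervention is delivered at those sessions. A patient recruited late in month 13 could not complete it within the chart on either clock.

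Two outcomes are exposed. Retention is part of the primary feasibility endpoint, and a patient whose visit falls after the close would look like a dropout when the cause is the calendar. The physical function tests are done only at 12 weeks, so a visit that is not made loses them altogether.

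**Working it through.** **Inputs.** Recruitment months 4–13, assessment close at the end of month 14, total 15 months, participation 12 weeks, entry 0 to 2 months after surgery (sections 7b and 7e); assessment at 12 weeks after surgery, 7 days of wear (section 7f); n = 50.

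**Conventions and assumptions.** One month = 4.348 weeks. Month k runs from k − 1 to k months elapsed, so recruitment spans 3.0 to 13.0. Even accrual is assumed: 50/10 = 5 per month.

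**Can the month-14 close be reproduced?** Counting from enrolment, the last recruit finishes at 13.0 + 12/4.348 = 13.0 + 2.76 = 15.76 months, or 13.0 + 13/4.348 = 15.99 with wear. Both fall in month 16, beyond the close and beyond the 15-month total. The stated close is not reproduced.

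**Formula.** With f weeks from entry to completion, the latest workable entry is L = 14 − f/4.348, and the number missing the close is 5 × (13 − L), or zero if L ≥ 13.

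**Clock from enrolment.**
- f = 12: L = 11.24; missed = 5 × 1.76 = 8.8 of 50.
- f = 13 (with wear): L = 11.01; missed = 5 × 1.99 = 9.9 of 50.

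**Clock from surgery.** For a patient entering s weeks after surgery, f = 12 − s, plus 1 with wear. If all patients entered at the same s:

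| s (weeks) | L, no wear | Missed of 50 | L, with wear | Missed of 50 |
|---|---|---|---|---|
| 0 | 11.24 | 8.8 | 11.01 | 9.9 |
| 2 | 11.70 | 6.5 | 11.47 | 7.6 |
| 4 | 12.16 | 4.2 | 11.93 | 5.3 |
| 6 | 12.62 | 1.9 | 12.39 | 3.0 |
| 8 | 13.08 | 0 | 12.85 | 0.7 |
| 8.7 | 13.24 | 0 | 13.01 | 0 |

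The very last recruit fits only if 12 − s ≤ 4.348, that is s ≥ 7.65 weeks, or s ≥ 8.65 with wear. The two-month eligibility limit is 8.70 weeks.

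If s is uniform over 0 to 8.70 weeks (an assumption; the documents do not give the distribution):
- No wear: 5 × (7.65/8.70) × 1.76/2 = 3.9 of 50.
- With wear: 5 × (8.65/8.70) × 1.99/2 = 4.9 to 5.0 of 50.
- Share of month-13 recruits missing the close: 63% (74% with wear). Share of month 12–13 recruits: 39% (49%).

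**If recruitment lasted 9 months, as section 7g says, and ended in month 12.** From enrolment, 76% of month-12 recruits would still miss the end of month 14. From surgery, two months remain after last entry, so everyone entering at 12 − 8.70 = 3.3 weeks or later fits (4.3 with wear).

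**The case against.** The strongest reply is that section 7f times the visit from surgery, so the interval from entry to assessment is shorter than 12 weeks for most patients and the shortfall could be nil. That stands, and it is why the range starts at zero. It does not rescue the chart, because the last recruit fits only at the very edge of the entry window.

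A second reply is that the timeline is an estimate, each phase ends on a count of 25 and not on a date, and no passage imposes a data cut-off at month 14. That also stands. If assessments ran to the end of month 15, the shortfall counted from enrolment would fall to 3.8 of 50 (5 × 0.76), or about 5 with wear. Counted from surgery, it would be zero for anyone entering at 3.3 weeks or later (4.3 with wear).

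Three stronger readings are tempting, and the documents do not support them:

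- **Most patients recruited in the last two months are lost.** This holds when counting from enrolment (88%, or 99.5% with wear, miss the close). Counting from surgery, it holds only if patients typically enter within about 3.3 weeks of surgery (4.3 with wear), and the documents do not say when they enter.
- **The loss falls on one arm.** Late recruits are all in phase 2, but in that phase Immediate sites deliver PATH-12 while Delayed sites deliver PATH. Both arms are thinned. Bias would need a further reason for unequal late accrual or loss.
- **Assessments starting in month 4 are impossible.** A patient entering at the start of month 4, two months after surgery, is due 3.3 weeks later, still in month 4.

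**Conclusion.** Figure 1 is inconsistent with the protocol's stated follow-up and should be corrected. Counted from enrolment, about 9 to 10 of 50 patients miss the month-14 close. Counted from surgery, the figure is roughly 0 to 10 of 50, with 4 to 5 under the assumed uniform entry. All these counts rest on even accrual over ten months; a recruitment pause for the washout would concentrate entry into fewer months and, if it fell before the last two, raise them.

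The consequence is conditional. If the close is enforced, 12-week data are missing and calendar loss is mixed with retention. If it is not, the data are late and overlap the analysis. Since the affected patients belong to the 25 in phase 2, a loss of 4 to 5 would be 16% to 20% of that phase. It reduces the information from that period without by itself biasing PATH against PATH-12.

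Two further mismatches need no assumption: 10 recruitment months in Figure 1 against 9 in section 7g, and a washout in section 7g that the chart does not show.

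**What to change.** 1. State one clock for follow-up, reconciling the 12 weeks of participation in section 7e with the 12 weeks after surgery in section 7f.
2. Reconcile the 9 and 10 recruitment months, show the washout in Figure 1 with its planned length, and reconcile the Intervention row with the course of therapy for the last recruits.
3. Restate the dates so that last entry plus 12 weeks plus 7 days falls before assessments close. Either option covers every permitted entry time on both clocks:
   - stop recruitment at the end of month 11 with assessments through month 14 (11 + 2.99 = 13.99); or
   - stop at the end of month 12, which gives section 7g's 9 months, with assessments through month 15 (12 + 2.99 = 14.99).
4. Start outcome analysis after the last monitor is returned.
5. Restate the monthly accrual needed.

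**Cost.** No extra patients or procedures. Before any washout, accrual rises from 5 per month to 50/8 = 6.3 under the first option or 50/9 = 5.6 under the second. If the washout took 4 to 6 weeks (an assumption borrowed from the background figure for outpatient rehabilitation; 0.9 to 1.4 months), these become 50/7.1 to 50/6.6 = about 7.1 to 7.6, and 50/8.1 to 50/7.6 = about 6.2 to 6.6. The first option leaves only month 15 for outcome analysis. The second pushes the analysis past the 15-month funded period.

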Following TKR, patients receive physical therapy either at home or at a skilled nursing rehabilitation facility and then transition to outpatient rehabilitation for 4-6 weeks.²⁰ The primary objective of therapy is to help the patient regain strength and mobility after surgery by strength and mobility exercises and functional training.²¹ Improved function is reported by 70-80% of patients and decreased pain is reported by 85-90% of patients receiving physical therapy.²² While physical therapists are effective at enhancing function and strength outcomes via rehabilitation exercises following TKR, encouraging patients to engage in the recommended 150 minutes/week of moderate-to-vigorous intensity physical activity during and after therapy is outside of their focus and not typically discussed.¹³

To date, only a few studies have focused on increasing overall physical activity levels in TKR patients; however, the increases in activity observed have been modest compared to changes observed in non-TKR populations and interventions were costly or resource intensive.²³⁻²⁵ Due to the high volume of contact time outpatient physical therapists have with TKR patients (2-3 times/week for 4-6 weeks) and the sense of rapport that is established between the therapist and patient,²¹ physical therapists may be a promising avenue to deliver a physical activity intervention. Given the success of physical therapists to achieve patient strength, mobility, and range of motion goals following TKR, it is likely that they could help patients increase their overall physical activity levels. TKR requires rehabilitation; thus, having physical therapists deliver a physical activity intervention during the required rehabilitation is a novel and efficient approach to reach patients and promote physical activity. *This research is significant because it is the first step towards building a progressive line of research targeting the development of a low-additional cost and translatable physical activity intervention that will have the ability to*

be widely disseminated by physical therapists providing rehabilitation, both in home or outpatient, to TKR patients.

Preliminary Studies:

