Aim 2: To examine the effect of a physical therapist led physical activity intervention on the changes in physical activity, physical function, and pain in TKR patients.

4) Setting

The study procedures will be performed at Palmetto Health USC Orthopedic Centers. Potential patients will be identified and recruited after they attend their first physical therapy appointment by physical therapists participating in the study. Patients who are interested in participating will complete the informed consent process with the Principal Investigator or study research assistants. Study data and consent forms will be stored in a locked office at Palmetto Health USC Orthopedic Centers and the University of South Carolina Technology Center to Promote Healthy Lifestyles.

5) Resources Available

The purpose of this study is to examine the feasibility of conducting a physical therapist led physical activity intervention in a clinical setting. We will strive to recruit a total of 50 patients. If recruitment efforts are slow, we will plan to recruit additional physical therapists to participate in the study and assist with recruitment over the 15 month granted funded period of time.

[name], the Principal Investigator and Assistant Professor in the Department of Exercise Science at USC, will oversee all study related procedures, included but not limited to recruitment, behavioral intervention, and data collection and analysis. [name] has extensive experience overseeing behavioral clinical trials.

[name], Co-Investigator and Senior Physical Therapist, will help recruit patients at Palmetto Health USC Orthopedic Centers and will coach participants as part of the intervention during standard physical therapy appointments.

[name], Co-Investigator and Clinical Psychologist, will serve as the mentor to [name] as well as oversee delivery and treatment fidelity of the behavioral intervention. Additionally, [name] serves as a PI for another study through Palmetto Health (Pro00033131 Promoting Health in Pregnancy and Postpartum).

All members of the study team will have a copy of the study protocol and know their respective research duties.

6) Prior Approvals

NA

7) Study Design

a. Recruitment Methods

Patients will be recruited from Palmetto Health USC Orthopedic Center. After completing the first outpatient physical therapy appointment, potentially eligible patients

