Treatment Fidelity. Due to the open, group-like nature of physical therapy and patient confidentiality, we are unable to audio record treatment sessions. Therefore, to monitor treatment fidelity to ensure intended session content for both conditions is delivered and that unintended session content (i.e., contamination such as goal setting on physical activity levels with a patient randomized to PATH-12) is not delivered, physical therapists will complete a session checklist. In addition, random observations will occur by USC research staff. The physical therapist and observation fidelity checklists will monitor session duration, goals set, and indication if aerobic physical activity was discussed.

h. Data and Specimen Banking

NA

i. Statistical Analysis

Descriptive statistics will be used to describe baseline characteristics, establish recruitment and retention rates, and examine intervention intensity (session frequency, duration, and fidelity) and patient and therapist satisfaction. Mixed ANOVA or ANCOVAs, if appropriate adjustments are required based on baseline characteristics, will examine the changes in physical activity levels (MVPA/week, steps/day), and pain (PROMIS and WOMAC) across time between PATH and PATH-12. Additionally, differences between PATH and PATH-12 in physical function (chair stands, Timed Up and Go, 6-minute walk) will be examined at 12 weeks. Although the proposed study may not be powered to detect significant differences, the results will allow us to collect feasibility and acceptability data, refine the intervention, if necessary, and determine effect sizes for future grant submissions.

j. Data Management

All surveys will be administered either on paper or online via REDCap (secure, web application for building and managing online surveys and databases – managed by the University of South Carolina). Paper surveys will be stored in a locked filing cabinet at Palmetto Health-USC Orthopedic Center or the TecHealth Center at University of South Carolina. All computer files will be password protected. Only the study team will have access to the data.

k. Confidentiality

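### Sections 7e and 7f give incompatible follow-up: 12 weeks of participation cannot hold if the final visit is 12 weeks after TKR and entry may be up to 2 months after TKR; weeks from TKR to baseline should be a prespecified covariate for the change outcomes

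*Combined protocol and SAP*

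**What the plan says.** **Duration.** Section 7e (Study Timelines): "Subject participation will last 12 weeks".

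**Visit timing.** Section 7f (Study Endpoints): "Assessments will be completed before the second outpatient therapy session (baseline) and at 12 weeks after TKR". Elsewhere the final visit is called only a 12-week visit, with no anchor and no visit window.

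**Entry.** Section 7b requires that patients "have had a knee replacement in the last 2 months". Under section 4 they are "recruited after they attend their first physical therapy appointment".

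**Therapy course.** The background text before Preliminary Studies describes outpatient therapist contact as "2-3 times/week for 4-6 weeks".

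**Analysis.** Section 7i plans "Mixed ANOVA or ANCOVAs, if appropriate adjustments are required based on baseline characteristics" for change in activity and pain. For function, "differences between PATH and PATH-12 in physical function (chair stands, Timed Up and Go, 6-minute walk) will be examined at 12 weeks", and section 7f adds "Only at 12 weeks will participants complete functional tests". Time since TKR is not named as an analysis variable.

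**The concern.** Sections 7e and 7f cannot both describe the same patient's follow-up. Either the stated duration is wrong or the final visit is not where 7f puts it.

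Two uses of the results depend on this. Retention is part of the primary feasibility endpoint, and retention over about 3 weeks is not comparable with retention over 10. The Aim 2 effect sizes are meant to support later grant applications, and a reader of 7e would take them as 12-week changes.

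Baseline is also taken at different points in recovery, and the change models use it as one time point. The adjustment rule in 7i depends on what the baseline data show, so an imbalance between arms in time since surgery may or may not be adjusted for.

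**Working it through.** **Inputs.** Final visit at 12 weeks after TKR (7f); baseline before the second outpatient session (7f); entry up to 2 months after TKR (7b); outpatient course of 4 to 6 weeks at 2 to 3 visits a week (background); 50 patients (7c). Let g be the weeks from TKR to baseline.

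**The plan's own figure.** Follow-up is 12 − g. It equals the 12 weeks of 7e only if g = 0, which cannot occur because patients are approached after an outpatient visit. If the final 7-day monitor wear starts at the visit and is counted, participation is 13 − g, which equals 12 only at g = 1. The stated figure is not reproduced in general.

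**Eligibility limit.** One month is 365.25/12/7 = 4.348 weeks, so two months is 8.70 weeks and 12 − 8.70 = 3.30 weeks. Taking two months as 62 to 59 days gives 3.14 to 3.57; taking it as 8 weeks gives 4.0. If baseline follows screening by one between-visit interval (1/3 or 1/2 week), the minimum is 3.30 − 0.33 = 2.97 or 3.30 − 0.50 = 2.80. About 3 weeks is a fair summary.

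**Follow-up and end of therapy by entry time** (course counted from g):

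| g (weeks) | Follow-up, 12 − g | With final wear, 13 − g | 4-week course ends, g + 4 | 6-week course ends, g + 6 |
|---|---|---|---|---|
| 2 | 10 | 11 | 6 | 8 |
| 4 | 8 | 9 | 8 | 10 |
| 6 | 6 | 7 | 10 | 12 |
| 8.7 | 3.3 | 4.3 | 12.7 | 14.7 |

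A 6-week course outlasts the final visit when g exceeds 6, and a 4-week course when g exceeds 8.

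**Chance imbalance in g (illustration).** The documents give no distribution of g. Assume it is uniform, with 25 patients per arm and clustering ignored.

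- Range 2 to 8.70 weeks: SD = 6.70/√12 = 1.93; SE of the arm difference = 1.93 × √(2/25) = 0.55; 95% range ±1.07 weeks.
- Range 0 to 8.70 weeks: SD = 8.70/√12 = 2.51; SE = 0.71; 95% range ±1.39 weeks.

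Clustering by site could widen both.

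**Cost of the covariate.** With two time points, the arm-by-time contrast is a comparison of change scores, so the covariate-by-time term adds one term to it. The variance factor for one uninformative covariate is (n − 3)/(n − 4) = 47/46 = 1.022, about 2%. Adjustment breaks even at R² = 1/47 = 0.0213, a correlation of about 0.15 with the change score.

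**The case against.** **The anchor is explicit.** Section 7f names surgery, and 7e is a one-line administrative duration, so the defect could be one loose sentence. Much of this stands. No passage schedules the final visit 12 weeks after enrolment. A reader of 7e might infer final visits at 14 to 20.7 weeks after TKR (12 + g for g from 2 to 8.7), but no assessment passage supports that. Figure 1 does not settle the matter either: it is a monthly chart and fits neither anchor fully.

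**Function tests.** A reader might infer that these are distorted by unequal recovery time and have no baseline to correct it. Under 7f everyone is tested at the same time after surgery, so that holds only if the visit is re-anchored on enrolment.

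**No outcome consequence is shown.** This stands as a limit. The documents give no recovery rate between surgery and week 12, so an imbalance in weeks cannot be turned into a bias in steps or MVPA, and none is claimed. Section 7i also already permits adjustment. But it permits it conditionally and names no variable, and naming one in advance is better than choosing after seeing the data.

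**Late entry may be rare.** This too stands: 3.3 weeks is what the criteria permit, not what is expected. A reader might infer that much of the PATH coaching is lost; the documents do not show this, and for anyone entering by week 6 even a 6-week course ends by the final visit. Nor are session counts shown to be cut short, since therapists record sessions as they occur (7g).

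**Participation length is loosely defined.** Monitors may be mailed (7f), and control patients get a coaching session after the assessment (7g), so 13 − g is approximate. Neither feature makes participation 12 weeks for all.

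**Conclusion.** The contradiction between 7e and 7f is certain from the text and should be corrected. Under the only stated anchor, follow-up runs from under 12 weeks down to about 3. The figures at given entry weeks are plain date arithmetic; how many patients fall at each is unknown.

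The covariate is a cheap improvement in the plan, not the repair of a demonstrated bias. It applies to the change outcomes, whose baselines fall at different recovery stages. The imbalance figures rest on an assumed uniform distribution and equal arms.

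The consequences fall on the meaning of retention and on the Aim 2 effect sizes. The other feasibility measures are not called into question.

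**What to change.** 1. Reconcile 7e and 7f to one anchor. If the surgery anchor is kept, replace the 12-week participation figure with 12 weeks minus the time from TKR to enrolment (about 3 weeks to under 12), plus the final 7-day wear if it starts at the visit.
2. In 7i, replace the conditional adjustment with a prespecified covariate, weeks from TKR to baseline, in the PATH versus PATH-12 comparisons of change in MVPA, steps and pain. Enter it as covariate-by-time in the mixed model, or as a covariate in ANCOVA. Time since TKR at the final visit would not serve, because under the surgery anchor it is nearly constant.
3. For the function tests, add the covariate only if the final visit is anchored on enrolment.
4. Report retention and change together with length of follow-up.

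**Cost.** Wording and one model term. No new data are needed, because screening already establishes time since TKR. If the covariate is uninformative, the loss is about one degree of freedom, roughly 2% in variance at n=50 (patient-level, clustering ignored). Keeping the surgery anchor also means stating openly that follow-up is unequal.

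### Seven days of baseline monitor wear does not fit between therapy sessions 1 and 2 at the stated visit rate, so planned coaching can fall inside the PATH baseline

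*Combined protocol and SAP*

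**What the plan says.** Section 7f (Study Endpoints) sets the deadline: "Assessments will be completed before the second outpatient therapy session (baseline"). The same paragraph says "Participants will also be given an Actigraph Link accelerometer and ActivPAL monitor to wear for 7 days at each assessment", and the table of measures marks both devices at baseline. On delivery it adds: "These monitors will be provided at the in-person assessment or mailed to the participants".

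Wear cannot begin before session 1. Section 4 (Setting) says "Potential patients will be identified and recruited after they attend their first physical therapy appointment", and section 7g (Screening) says "Participants will be required to complete a brief screening after the first physical therapy appointment". Consent may come later still: section 7a allows it "either at the first or second outpatient physical therapy appointment", whereas section 13 (Consent Process) puts it after the first or before the second appointment.

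The background section gives outpatient contact as "2-3 times/week for 4-6 weeks". The study's own interval between sessions 1 and 2 is not stated.

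Under Randomized Conditions in section 7g, PATH therapists discuss activity at every session and set a goal at least weekly. PATH-12 therapy is left unchanged, with one coaching session after the 12-week assessment. Section 7f sums MVPA across the week, defines a valid day by wear time only, and asks for wear logs. Section 7i compares change in MVPA/week and steps/day between arms by mixed ANOVA or ANCOVA, and intends to derive effect sizes for later grant applications.

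**The concern.** A baseline should describe patients before the two arms begin to differ. Here the device week can start no earlier than session 1, and by plan the arms differ from the first coached session onward. If that session falls inside the wear week, the PATH baseline contains coached days and the PATH-12 baseline does not. Any early response to coaching is then counted as starting level and subtracted from the PATH change.

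If coaching raises activity, the error runs one way, toward no difference. Aim 2 concerns change in physical activity, and an effect size that is too small could mis-size the next trial. The surveys take about 20 minutes and can be finished before session 2, so the conflict concerns the devices only.

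**Working it through.** The plan gives no power calculation or expected effect, so there is no figure to reproduce. The check is calendar arithmetic, followed by an illustration of bias.

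**1. Gap between sessions.** At k sessions per week the mean gap is g = 7/k: 7/2 = 3.5 days and 7/3 = 2.33 days.

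**2. Share of the wear week after session 2.** With wear starting t days after session 1, share = (7 − max(0, g − t))/7.

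| Start of wear | g = 3.5 | g = 2.33 |
|---|---|---|
| t = 0 (at session 1) | 50% | 67% |
| t = 2 (mailed, assumed transit) | 79% | 95% |
| t = 3 (mailed, assumed transit) | 93% | 100% |

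With t = 0, a 6-day gap gives 1/7 = 14%, and a gap of 7 days or more gives 0%.

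**3. Individual schedules.** Over every regular Monday-Friday pattern, the gap runs from 1 to 6 days at two sessions per week and from 1 to 5 days at three. In whole days, with the day of session 2 counted as after, that leaves 0-5 full wear days before session 2 and 2-7 on or after it. No pattern leaves 7 before.

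**4. Bias.** Let r be the early effect as a fraction of the 12-week effect. The documents do not give r.

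- Change score (with two time points, the group-by-time test of a mixed ANOVA is the same contrast): proportional loss = share × r.
- ANCOVA with baseline activity as covariate: loss = slope × share × r.

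The slope is an assumption. Take a single-day ICC of 0.5 and a true correlation of 0.6. The reliability of a 7-day mean is 7 × 0.5/(1 + 6 × 0.5) = 0.875, the observed correlation is 0.6 × 0.875 = 0.525, and with equal SDs this is the slope.

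| r | Change score (share 0.50 to 0.667) | ANCOVA (× 0.525) |
|---|---|---|
| 0 | 0 | 0 |
| 0.25 | 12-17% | 7-9% |
| 0.5 | 25-33% | 13-18% |

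**5. Price of a shorter baseline.** With k baseline days, reliability is rel_k = 0.5k/(1 + 0.5(k − 1)) and ρ_k² = 0.36 × rel_k × 0.875. This gives ρ² = 0.1575, 0.2100, 0.2363 and 0.2756 for k = 1, 2, 3 and 7. The rise in SE against the full week is √[(1 − ρ_k²)/(1 − 0.2756)] − 1 = 7.8%, 4.4% and 2.7% for 1, 2 and 3 days. With no baseline it is 1/√0.7244 − 1 = 17.5%. Site clustering is ignored.

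**6. Bias against variance.** Assume 25 per arm and a 12-week effect of 0.5 SD. Cutting to 1-3 days adds variance of (2/25) × (0.2756 − ρ_k²) = 0.009 (1 day) to 0.003 (3 days). The squared ANCOVA bias removed is (0.5 × loss)²: 0.001-0.002 at r = 0.25 and 0.004-0.008 at r = 0.5. Truncation therefore loses at r = 0.25 and roughly breaks even at r = 0.5.

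**7. Fragility of MVPA.** In Table 1 of the preliminary studies the SD is 138-229% of the mean for MVPA (108.0/78.1 to 76.4/33.3) and 33-58% for steps/day (1653.2/4943.6 to 2910.2/4991.8). The SE figures in step 5 therefore suit steps better than MVPA.

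**The case against.** Completing baseline before session 2 can be read as surveys done and monitors handed out, with wear to follow. That removes the contradiction in wording but not the overlap, because wear then runs through session 2 and beyond.

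The visit rate comes from general background, not a study schedule, and the plan does not name the first coached session. Both points stand. A patient whose second visit came 7 or more days after wear began would comply, and coaching from session 2 is an inference from its delivery at every session.

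Four stronger readings are tempting, and the documents do not support them:

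- *The whole baseline week is coached.* This needs monitors issued at session 2. Only section 7a allows consent that late; section 13 and the deadline in section 7f point the other way.
- *Only PATH can be exposed.* That is the planned content. Treatment Fidelity in section 7g expects possible activity goal setting with PATH-12 patients and monitors for it.
- *A quarter to a third of the effect is lost.* That needs r = 0.5 and a raw change score. Section 7i also allows ANCOVA, though it does not name baseline activity as the covariate.
- *A baseline cut at session 2 should be the main analysis.* Steps 5 to 7 show a trade-off, not a clear gain.

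The stakes are also bounded. Feasibility is the primary endpoint, and the plan says it may lack power for group differences.

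**Conclusion.** The timing conflict is real at the documents' own visit rate and does not depend on any assumed effect. With wear from session 1, an average of 50-67% of the baseline week follows session 2, and more if monitors are mailed. No stated rule separates coached from uncoached days.

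The resulting bias is conditional. It requires coaching to start while monitors are worn and to raise activity within days. Its direction is then toward zero; its size is unknown and may be nil. The illustrative losses rest on r = 0.25 or 0.5 and, for ANCOVA, a slope of 0.525, none of which the documents supply.

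The concern reaches the device-measured secondary outcomes and the effect sizes taken from them. It does not reach the feasibility endpoint, the surveys or the 12-week function tests. The plan should be changed because the repair is cheap; confidence is medium.

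**What to change.** 1. Reconcile sections 7a, 7f, 7g and 13 on when consent, baseline wear and first coaching occur relative to one another. The timing of coaching is for the investigators.
2. Make sure that wear logs, session records and fidelity checklists carry dates. Flag each baseline wear day as before or after session 2, in the same way in both arms.
3. Analyse 12-week activity with baseline as an ANCOVA covariate, not as a raw change score. At the assumed slope this roughly halves any such bias; it does not remove it.
4. Unless wear is completed before coaching starts, add two sensitivity analyses: one whose baseline uses only valid days before session 2, per valid day and with the same cut-off in both arms, and one comparing 12-week values without baseline. Report how many patients per arm have no such day, and state that the full-week contrast may be attenuated.

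The cost is wording, dated forms and a little analysis; no visit or device is added. The sensitivity results will be less precise: under the assumptions in step 5, the SE rises about 3-8% with 1-3 baseline days and 17-18% with none. MVPA scaled up from a single day is fragile, so the truncated baseline need not be the main analysis.
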